**Table 6-3: Dose Modification Criteriaa**

Toxicity Criteria	Recommended Guidelines for Management
Grade 1 AEs	
 
Continue study treatment if AE is tolerated
 

Grade 2 AEs which are intolerable and cannot be adequately managed	
 
At the discretion of the investigator, study treatment should be dose reduced or interrupted.
 
 
Note: It is recommended that dose interruptions be as brief as possible.

Grade 3 (except clinically non-relevant laboratory abnormalities)	
 
Study treatment should be interrupted unless the toxicity can be easily managed with a dose reduction and optimal medical care.
 

Grade 4 AEs (except clinically non-relevant laboratory abnormalities)	
 
Subjects should have their study treatment interrupted immediately.
 
 
Discontinue study treatment unless the following criteria are met:
 
Subject is deriving clear clinical benefit as determined by the investigator and agreed by the Sponsor
 
Toxicity can be managed with a dose reductionb following recovery to Grade 1 (or baseline) and optimal medical care

AE, adverse event.

**Note:** The dose delay and modification criteria for specific medical conditions are provided in Section 6.7. For re-treatment criteria of study treatment after a dose hold see Section 6.5.1.1.

a Study treatment dose adjustment is only needed if the toxicity was deemed related to study treatment or had an unclear relationship to study treatment.

b For dose reduction levels, see Table 6-4.

**Table 6-4: Dose Reductions**

Assigned dose	First Dose Level Reduction	Second Dose Level Reduction
60 mg of study treatment oral qd	40 mg of study treatment oral qd	20 mg of study treatment oral qd

qd, once daily

All study treatment must be discontinued if a qd dose of 20 mg cabozantinib/matched placebo (minimum dose) is not tolerated

If the study transitions to the Open-Label Phase, study treatment will be unblinded and dose modifications will occur in an open-label fashion.

### **6.5.1.1 Dose Reinstitution and Reescalation**

If the subject recovers from his or her AEs to CTCAE v.4.0 Grade  $\leq$  1 or to the baseline value (or lower) and the AE was unrelated to study treatment, then study treatment may be restarted with no change in dose.

If the subject recovers from his or her AEs to Grade  $\leq$  1 or to the baseline value (or lower) the toxicity was deemed possibly related to study treatment, then study treatment may be restarted at a reduced dose (see Table 6-4 for the schedule of dose reductions). Subjects receiving a daily dose of 20 mg may be restarted at the same dose if deemed safe at the discretion of the investigator. Subjects unable to tolerate a daily dose of 20 mg will discontinue study treatment.

Re-escalation to the previous dose, (but not higher than 60 mg/day) may be allowed at the discretion of the investigator and agreement of the Sponsor but no sooner than 2 weeks beyond resolution of AEs that led to the dose reduction. Dose re-escalation is not allowed for a dose reduction triggered by myelosuppression or by Grade 4 AEs affecting major organs (eg, central nervous system, cardiac, hepatic, renal).

## **6.6 Best Supportive Care (BSC)**

To ensure that BSC is equally available to all subjects entered into the trial, subjects will be seen and evaluated every 2 weeks up to Week 9 and then every 4 weeks thereafter as outlined in Section 5.2. Interval history and indicated physical examinations and laboratory tests will be monitored regularly and equally for all subjects, permitting prompt recognition of abnormalities. Treatment with BSC will be instituted promptly, as clinically appropriate, for all subjects with symptoms or complications.

General guidelines for other aspects of BSC are found in Appendix F.

## **6.7 Warnings, Precautions, and Guidelines for Management of Potential Cabozantinib Adverse Events**

### **6.7.1 General**

The side effect profile of cabozantinib includes GI symptoms (such as nausea, vomiting, and diarrhea, mucositis/stomatitis), fatigue/asthenia, anorexia, weight loss, skin disorders including PPE syndrome, elevated liver function tests (including alanine aminotransferase [ALT] and AST), increased pancreatic enzymes with rare cases of overt pancreatitis, hypothyroidism, QTc prolongation, as well as side effects associated with inhibition of VEGF signaling. The latter of these include arterial and venous thrombotic events such as deep vein thrombosis (DVT),

pulmonary embolism (PE), transient ischemic attack, and myocardial infarction; hypertension; hemorrhagic events; proteinuria, wound complications, and rare cases of GI perforation, fistulae formation and rectal/perirectal abscess, osteonecrosis, and reversible posterior leukoencephalopathy (RPLS). Please refer to the Investigator's Brochure for additional details.

As with all investigational products, unknown AEs may occur. Subjects should be monitored closely throughout their study participation for all AEs. As with other agents in development, additional AEs are unknown. As of 22 October 2013, in studies with cabozantinib, angioedema has been reported to occur in ~0.1% of subjects treated.

The predicted effective plasma half-life of cabozantinib is 55 hours. Thus, when initiating therapy with cabozantinib, it will take most subjects 2-3 weeks to reach steady state after daily dosing. If AEs attributable to cabozantinib occur within the initial 3-week period of dosing, early intervention with dose modifications may be justified for AEs that, if worsened, could potentially be dangerous or debilitating, since without a dose adjustment, systemic exposure of cabozantinib might be expected to increase after the onset of the AE.

Management of fatigue, anorexia, diarrhea, nausea, skin disorders, vomiting, rash, hypertension, proteinuria, elevated ALT and AST, myelosuppression, mucositis, hypothyroidism, and cardiac disorders are presented in this section as these have been observed in previous studies with cabozantinib or represent common class effect toxicity. In addition, guidelines to minimize the risk for potential SAEs such as GI and non-GI perforation and fistula formation, hemorrhagic events, and osteonecrosis of the jaw (ONJ) are provided in this section.

Please refer to the Investigator's Brochure for additional practice guidelines and management recommendations for side effects potentially related to cabozantinib treatment; available information on potential risk of congenital, familial, and genetic disorders; and guidelines on management of cabozantinib overdose.

### **6.7.2 Gastrointestinal Disorders**

The most common GI AEs reported in clinical studies with cabozantinib are diarrhea, oral pain, dyspepsia, stomatitis, and dysphagia.

#### Diarrhea

Subjects should be instructed to notify their physician immediately at the first signs of poorly formed or loose stool or an increased frequency of bowel movements. Administration of

antidiarrheal/antimotility agents is recommended at the first sign of diarrhea as initial management. Some subjects may require concomitant treatment with more than one antidiarrheal agent. When therapy with antidiarrheal agents does not control the diarrhea to tolerable levels, study treatment should be temporarily interrupted or dose reduced per Table 6-3.

In addition, general supportive measures should be implemented including continuous oral hydration, correction of fluid and electrolyte abnormalities, small frequent meals, and stopping lactose-containing products, high fat meals and alcohol.

For more information please refer to the current Investigator's Brochure.

### Nausea and Vomiting

Antiemetic agents are recommended as clinically appropriate at the first sign of nausea and vomiting or as prophylaxis to prevent emesis, along with supportive care according to clinical practice guidelines. The 5-HT3 receptor antagonists are recommended over chronic use of NK-1 receptor antagonists and dexamethasone (NK-1 receptor antagonists can induce or inhibit CYP3A4, and glucocorticoids induce CYP3A4 and thus could lower cabozantinib exposure (see Section 7.1.2.1). Caution is also recommended with the use of nabilone, which is a weak inhibitor of CYP3A4.

### Stomatitis and Mucositis

Preventive measures may include a comprehensive dental examination to identify any potential complications before study treatment is initiated. Removal of local factors should be instituted as indicated, such as modification of ill-fitting dentures and appropriate care of gingivitis.

During study treatment good oral hygiene and standard local treatments such as nontraumatic cleansing and oral rinses (eg, with a weak solution of salt and baking soda) should be maintained. The oral cavity should be rinsed and wiped after meals, and dentures should be cleaned and brushed often to remove plaque. Local treatment should be instituted at the earliest onset of symptoms. Obtain bacterial/viral culture if oral infection is suspected and treat infection as clinically indicated. When stomatitis interferes with adequate nutrition and local therapy is not adequately effective, dose reduction or temporary withholding of study treatment should be considered.

### **6.7.3 Hepatobiliary Disorders**

Elevations of ALT, AST, and total bilirubin have been observed during treatment with cabozantinib.

A subject who has ALT, AST, and total bilirubin  $\leq 3.0 \times \text{ULN}$  at baseline and who develops  $\geq$  Grade 3 elevated ALT, AST, or total bilirubin should have study treatment interrupted and the dose reduced as outlined in Tables Table 6-3 and Table 6-4.

Subjects on this study may enter the study with elevations of AST/ALT up to  $5 \times \text{ULN}$  at baseline. Elevations of aminotransferases when hepatic tumors are present may not require dose modifications if there are no progressive changes in the aminotransferases (less than a doubling) and if there are no progressive elevations in serum total bilirubin concentration or coagulation factors. Cabozantinib treatment should be interrupted when transaminase increases are accompanied by progressive elevations of total bilirubin, and/or elevations of coagulation tests (eg, International Normalized Ratio [INR]). More frequent monitoring of transaminases should be considered and study treatment should be held until the etiology of the abnormalities is determined and these abnormalities are corrected or stabilize at clinically acceptable levels. If hepatic toxicity resolves during a temporary hold and was deemed related to study treatment, then study treatment may be restarted at a reduced dose. Study treatment should be discontinued if hepatic dysfunction is not reversible despite temporary interruption of study treatment. Elevations  $> 3 \times \text{ULN}$  of ALT or AST concurrent with  $> 2 \times \text{ULN}$  total bilirubin without other explanation can indicate drug-induced liver injury and drug should be permanently discontinued.

If possible, hepatotoxic concomitant medications should be discontinued in subjects who develop increased values of ALT, AST, or total bilirubin.

Evaluation of subjects with elevated transaminases or total bilirubin should be individualized and guided by the presence of specific risk factors such as illnesses which affect liver function (eg, infectious and non-infectious causes of hepatitis, liver cirrhosis, thrombosis of portal or hepatic vein), concomitant hepatotoxic medication, alcohol consumption, and cancer related causes. AEs which are based on hepatic dysfunction should be managed according to locally accepted clinical practice, including monitoring of appropriate laboratory functions.

### **6.7.4 Hematological Disorders**

Hematological toxicities (ie, neutropenia and thrombocytopenia) and associated complications have been observed after administration of cabozantinib and may be managed with dose

interruptions and/or dose reductions. Use of granulocyte colony-stimulating factor support for neutrophil recovery is allowed per investigator discretion in accordance with the American Society of Clinical Oncology Guidelines.

Complete blood counts with differentials and platelets should be performed during treatment on the schedule indicated in Appendix A. Subjects with hematologic toxicities may require additional or more frequent laboratory tests according to institutional guidelines.

Febrile neutropenia or evidence of infection associated with neutropenia must be assessed immediately and treated aggressively according to institutional guidelines.

Dose reductions or dose interruptions for anemia are not mandated but can be applied as clinically indicated. Supportive care such as red blood cell transfusions may be given as clinically indicated.

#### **6.7.5 Fatigue, Anorexia, and Weight Loss**

Fatigue has been reported during treatment with cabozantinib. Common causes of fatigue such as anemia, deconditioning, emotional distress (depression and/or anxiety), nutrition, sleep disturbance, and hypothyroidism should be ruled out and/or these causes treated according to standard of care. Individual nonpharmacological and/or pharmacologic interventions directed to the contributing and treatable factors should be given. Pharmacological management with psychostimulants such as methylphenidate should be considered after disease specific morbidities have been excluded. Note: Chronic use of modafinil should be avoided because of its potential to reduce cabozantinib exposure (see Investigator's Brochure).

Dose reduction of study treatment should be considered when general or pharmacological measures have not been successful in reducing symptoms. Dose interruption may be considered for Grade  $\geq 3$  fatigue despite optimal management, at the investigator's discretion.

Anorexia and weight loss should be managed according to local standard of care including nutritional support. Pharmacologic therapy such as megestrol acetate should be considered for appetite enhancement. Should these interventions prove ineffective, dose hold and reductions may be considered for Grade  $\geq 3$  anorexia or weight loss. If anorexia and/or weight loss do not recur after a dose reduction, dose of study treatment may be reescalated to the previous dose.

## 6.7.6 Skin Disorders

### Palmar-plantar erythrodysesthesia (PPE) syndrome

PPE syndrome (also known as hand-foot syndrome), skin rash (including blisters, erythematous rash, macular rash, skin exfoliation, dermatitis acneiform, and papular rash), pruritus, dry skin, and erythema have been reported in cabozantinib-treated subjects. All subjects on study should be advised on prophylactic skin care. This includes the use of hypoallergenic moisturizing creams, ointment for dry skin, and sunscreen with sun protection factor  $\geq 30$ ; avoidance of exposure of hands and feet to hot water; protection of pressure-sensitive areas of hands and feet; and use of thick cotton gloves and socks to prevent injury and to keep the palms and soles dry. Subjects with skin disorders should be carefully monitored for signs of infection (eg, abscess, cellulitis, or impetigo).

Early signs of PPE syndrome include tingling, numbness, and slight redness or mild hyperkeratosis. Early manifestations include painful, symmetrical red and swollen areas on the palms and soles. The lateral sides of the fingers or peri-ungual zones may also be affected. Adequate interventions are required to prevent worsening of skin symptoms such as blisters, desquamations, ulcerations, or necrosis of affected areas. Aggressive management of symptoms is recommended, including early dermatology referral. Treatment guidelines for PPE related to blinded study drug (referred to as “study treatment”) are presented in Table 6-5.

In the case of study treatment-related skin changes, the investigator may request that additional assessments be conducted with the subject’s consent. These assessments may include digital photographs of the skin changes and/or a biopsy of the affected skin and may be repeated until the skin changes resolve.

**Table 6-5: Dose Modification Criteria and Recommended Guidelines for Treatment-emergent PPE Syndrome**

CTCAE v.4.0 Grade	Action To Be Taken
Grade 1	
 
Study treatmenta may be continued at the current dose if PPE syndrome is clinically insignificant and tolerable. Otherwise, study treatmenta should be reduced to the next lower dose level. Start urea 20% cream twice daily AND clobetasol 0.05% cream once daily. Reassess at least weekly; if PPE syndrome worsens at any time or does not improve after 2 weeks, proceed to the intervention guidelines for Grade 2.
 

Grade 2	
 
Study treatmenta may be continued if PPE is tolerated. Study treatment should be dose reduced or interrupted if PPE is intolerable. Continue urea 20% cream twice daily and clobetasol 0.05% cream once daily and add analgesics (eg, NSAIDs/gamma-aminobutyric acid agonists) for pain control if needed. Reassess at least weekly; if PPE does not improve within 2 weeks or worsens or affects self-care, proceed to the intervention guidelines for Grade 3.
 

Grade 3	
 
Interrupt study treatmenta until severity decreases to Grade 1 or 0. Continue treatment of skin reaction with clobetasol 0.05% cream twice daily AND analgesics. Resume study drug at a reduced dose if PPE syndrome recovers to Grade <math>\leq 1</math>. Discontinue subject from study if intolerable PPE syndrome recurs at a reduced dose or if PPE syndrome does not improve within 6 weeks.
 

CTCAE, Common Terminology Criteria for Adverse Events; GABA, gamma-amino butyric acid; NSAID, non-steroidal anti-inflammatory drug; PPE, Palmar Plantar Erythrodysesthesia.

a Study treatment includes both cabozantinib and matched placebo.

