#### **1.4.2 Rationale for Study Design**

There are no approved therapies for the second-line treatment of HCC after progression following sorafenib. The guidelines of the National Comprehensive Cancer Network (NCCN 2011) recommend best supportive care (BSC) or a clinical trial for this patient population. Furthermore, EORTC guidelines specifically recommend that second-line trials should be designed as placebo-controlled randomized trials.

This is a randomized, double-blinded, controlled study of cabozantinib vs placebo for the treatment of HCC in subjects previously treated with sorafenib. Placebo has been chosen as the comparator in this study due to the lack of available second-line treatments for HCC. The 2:1 randomization was selected as an incentive for subject participation in a placebo-controlled trial. All subjects will receive BSC in addition to the randomized study treatment (Appendix F).

OS is the primary efficacy endpoint, with ORR and PFS as secondary endpoints. OS is an accepted regulatory and clinical endpoint and is the most appropriate endpoint for this population. In order to avoid confounding the OS endpoint, crossover to cabozantinib will not be permitted in this study.

In addition, the standardized measure of health status EQ-5D-5L, developed by the EuroQol group, will be used in order to provide a generic measure of health for clinical appraisal (Herdman 2011). The questionnaire will be self-completed by the subjects. The objective will be to assess the time to deterioration of these outcomes as an endpoint supportive of the primary endpoint rather than to ascertain a treatment-related improvement in quality of life.

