### 7.1.2 Prohibited or Restricted Therapies

The following therapies are prohibited while the subject is on study treatment:

- any investigational agent or investigational medical device
- any drug or herbal product used specifically for the treatment of HCC
- therapeutic doses of oral anticoagulants (eg, warfarin or warfarin-related agents, thrombin or FXa inhibitors, antiplatelet agents such as clopidogrel)
- interferon treatment

Liver-directed local anti-cancer therapy (eg, transarterial tumor embolization or chemoembolization, radiofrequency or microwave ablation, percutaneous ethanol or acetic acid ablation, injection or infusion of drug eluting or radiation-emitting beads, cryoablation, radiation therapy [including stereotactic radiotherapy], or surgery) or systemic anticancer therapies are not permitted on study treatment. If a subject requires additional systemic anticancer treatment or liver-directed local anti-cancer therapy, study treatment must be discontinued. Palliative external radiation to bone metastasis or skin/subcutaneous metastasis, is allowed but discouraged unless medically unavoidable. Subjects who have such intervention may be considered inevaluable for certain efficacy endpoints.

Erythropoietic-stimulating agents (eg, epoetin alfa and darbepoetin alfa) should not be used based on a report of increased risk of tumor recurrence/progression associated with erythropoietin (Wright 2007).

The chronic co-administration of strong CYP3A4 inducers should be avoided (Section 7.1.2.1). Other drugs that induce CYP3A4 should be used with caution because these drugs have the potential to decrease exposure (AUC) to cabozantinib. Selection of alternate concomitant medications with no or minimal CYP3A4 enzyme induction potential is recommended.

Caution must be used when discontinuing treatment with a strong CYP3A4 inducer in a subject who has been concurrently receiving a stable dose of cabozantinib, as this could significantly increase the exposure to cabozantinib.

Coadministration of strong CYP3A4 inhibitors and other drugs that inhibit CYP3A4 should be avoided because these drugs have the potential to increase exposure (AUC) to cabozantinib (Section 7.1.2.1). Selection of alternate concomitant medications with no or minimal CYP3A4 enzyme inhibition potential is recommended.

Additional information on potential drug interactions with cabozantinib is provided in Section 7.1.2.1.

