## **Appendix F: Guidelines for Best Supportive Care**

The following general guidelines should be utilized to provide subjects with BSC:

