### ***Analgesia***

- Pain assessment with prescriptions for nonnarcotic or narcotic analgesics, as required, except that nonsteroidal anti-inflammatory agents should not be used in treatment of pain, because they are known to induce renal failure in patients with decompensated liver disease
- Management of toxicities from analgesic medication including constipation, nausea or gastritis

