### ***Liver decompensation***

- GI bleeding, hepatic encephalopathy, ascites, and bacterial infections should be treated as in patients with nonneoplastic liver disease

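### Table 6-5 offers NSAIDs as an example analgesic for hand-foot syndrome pain, while Appendix F says NSAIDs should not be used for pain

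*Protocol*

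**What the plan says.** Protocol Section 6.7.6 gives graded management advice for PPE in Table 6-5. In the Grade 2 row, besides the topical creams, the investigator is to "add analgesics (eg, NSAIDs/gamma-aminobutyric acid agonists) for pain control if needed". Grade 1 cases can also reach this row: "if PPE syndrome worsens at any time or does not improve after 2 weeks, proceed to the intervention guidelines for Grade 2". The Grade 3 row calls for analgesics without naming any and without pointing elsewhere. A footnote to the table says that study treatment covers both cabozantinib and matched placebo.

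Appendix F opens with "The following general guidelines should be utilized to provide subjects with BSC". Under Analgesia it allows nonnarcotic or narcotic drugs as required, "except that nonsteroidal anti-inflammatory agents should not be used in treatment of pain". The reason it gives is renal failure in patients whose liver disease is decompensated.

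Section 1.4.2 says that all subjects receive best supportive care on top of randomized treatment and cites Appendix F. Section 6.6 adds "General guidelines for other aspects of BSC are found in Appendix F".

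**The concern.** One part of the protocol suggests a drug class for pain and another part says not to use that class for pain. A site that takes up the Table 6-5 example acts against the supportive care guideline that applies to the same subject. A site that works from Table 6-5 alone sees no warning, because the table carries no caveat about liver function.

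The stake is subject safety, not inference. Every subject has HCC. They enter with compensated liver function, but Appendix F foresees decompensation and says how to manage it: "GI bleeding, hepatic encephalopathy, ascites, and bacterial infections should be treated as in patients with nonneoplastic liver disease". Decompensation is the setting of its NSAID warning.

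**Working it through.** No arithmetic applies to the main point. The check is a comparison of texts, followed by a search for anything that reconciles them.

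1. **Same drug class.** The abbreviation key under Table 6-5 expands NSAID to the class that Appendix F names in full.
2. **Same purpose.** Both sentences are about treating pain.
3. **Same subjects.** Appendix F applies to all subjects (Section 1.4.2). Section 6.6 has supportive care started for any subject with symptoms or complications, which on its face includes PPE pain. Table 6-5 covers both arms by its footnote.
4. **Opposite advice.** Table 6-5 gives NSAIDs as one of two example classes. Appendix F says they should not be used.
5. **Scope of the Appendix F sentence.** Decompensated liver disease appears in the reason, not in the instruction. The instruction is not confined to decompensated subjects and has no PPE exception.
6. **Search for a reconciling text.** Section 7.1.1 (allowed therapies) does not mention NSAIDs. Section 7.1.2 introduces its list with "The following therapies are prohibited while the subject is on study treatment", and NSAIDs are not on it. So the problem is conflicting advice between two guidelines, not a breach of a listed prohibition. No section states an order of precedence.
7. **Other mention of the class.** Section 6.7.12 lists chronic NSAID use among additional risk factors for gastrointestinal perforation or fistula, a diagnosis that ends all study treatment. This covers chronic use only, but it does not depend on decompensation.
8. **Liver status at entry.** Section 4.2 requires Child-Pugh A, which Appendix E sets at 5 to 6 points. Slight ascites scores 2, and the other four items score at least 1 each, so 2 + 4 × 1 = 6 is still class A. Section 4.3 excludes only moderate or severe ascites. Entry as Child-Pugh A therefore does not mean the absence of every sign of liver impairment.
9. **Will the table be used?** Any-grade PPE was reported in 54% of the 41 HCC subjects in Study XL184-203, who started at 100 mg, with Grade 3 or higher in 15% (Section 1.3.3.3.1). In the pooled single-agent data, 2410 subjects, it was 35% (Section 1.3.3.1). These rates show only that sites will consult the table. They are not rates of painful PPE, of NSAID use or of decompensation, none of which the documents give.

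**The case against.** The best case for leaving the text alone has four parts.

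- **Section 6.7 is the specific guidance.** Section 6.5.1 sends the reader to Section 6.7 for particular adverse events, skin disorders included, while Section 6.6 and Appendix F call their content general. One can read Table 6-5 as governing drug-related skin toxicity. That reading is fair, but no sentence says so, and the Appendix F wording on pain has no carve-out.
- **The stated hazard does not describe subjects at entry.** They are Child-Pugh A, with bilirubin at most 2 mg/dL, albumin at least 2.8 g/dL and no more than slight ascites. If liver function worsens, Section 6.7.3 provides for interrupting or stopping study treatment, and serum chemistry including creatinine is scheduled every 2 weeks through Week 9 and every 4 weeks after that. These safeguards stand and lower the risk. They do not tell a site which analgesic advice to follow.
- **It is only an example, to be used if needed.** This is correct, and a site can comply with both texts by using another analgesic. It is the main reason the point is minor.
- **Deleting NSAIDs takes a side that the documents do not take.** The conflict could also be resolved by limiting the Appendix F instruction to decompensated subjects. That is a legitimate alternative if the sponsor judges NSAIDs acceptable in compensated disease, provided both places then say so.

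Taken together, these arguments limit the severity but do not remove the contradiction.

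**Conclusion.** The concern holds as a minor inconsistency in safety guidance. Two current texts give opposite advice on the same drug class, for the same purpose, in the same subjects, and nothing in the protocol settles it.

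The size of any harm is not estimable: the documents give no rate of PPE pain needing analgesics, of NSAID use, or of decompensation on study. Sample size, alpha, power and the overall survival analysis are unaffected.

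The conclusion rests on reading the Appendix F instruction as written, with decompensation as its reason and not as its limit. If the sponsor meant it as a limit, the wording still needs correcting, but in Appendix F and with a matching caveat in Table 6-5.

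**What to change.** In the Grade 2 row of Table 6-5, remove NSAIDs from the example, keep gamma-aminobutyric acid agonists, and add a reference to Appendix F for the choice of analgesic. Add the same reference to the analgesic instruction in the Grade 3 row. This is the cautious choice and agrees with the Section 6.7.12 warning on chronic use. If the sponsor wants to keep NSAIDs available for compensated subjects, Table 6-5 and Appendix F should both state the condition in the same terms.

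The cost is an edit to one table (two places in the alternative), sent with a site letter or the next amendment. It adds no procedures or data collection and does not change the sample size or the analysis.
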